10 STATISTICAL ANALYSIS

10.1 Descriptive statistics

Descriptive statistic of all the variables collected in the Data Collection Notebook, with frequency tables for nominal variables and measures of central tendency and dispersion for the continuous variables. 95% confidence intervals (95% CI) will be estimated for the latter.

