7.4 Number of subjects

The number of subjects expected for this pilot study is 30 women.

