7.5 Rationale of sample size

In an exploratory pilot study to test a concept, it has been estimated that 30 patients will be sufficient to analyze results.

Being a pilot study, it is understood that the estimation of the sample size is not necessary.

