9 STUDY MEASUREMENTS AND ENDPOINTS

9.1 Study endpoints

9.1.1 Primary endpoint

Differences in trabecular structure of subcutaneous tissue between the time prior to the multidisciplinary treatment and after the end of the treatment, assessed by skin ultrasound:

- Indented subcutaneous fascicles in the dermis (length: measured from the center of the base to the point of maximum indentation in the dermis)

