10.2 Analysis of objectives

For the analysis of the primary objective, we will study the mean values of the trabecular structure and skin thickness, comparing the results before and after treatment. Similarly we will compare the scores of the photographic images (overall score and scores of each scale). Qualitative variables will be compared using Fisher's exact test, and the quantitative variables will be compared by means of the student's t test (in the case of 2 groups) or by the one-way ANOVA test (for 3 or more groups). If the conditions of the Student t test or the Anova test are not met, we will use the non-parametric test of the Mann-Withney U (2 groups) or the Kruskall-Wallis test (for 3 or more groups).

For all tests, the significance level will be set at $p < 0.05$.

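### The primary endpoint is a within-woman change, but the plan specifies no SD or 95% CI for that change and no interval for the change in edema or nodules

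*Combined protocol and SAP*

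**What the plan says.** - **Endpoint.** Section 9.1.1 defines the primary endpoint as "Differences in trabecular structure of subcutaneous tissue between the time prior to the multidisciplinary treatment and after the end of the treatment", measured as the length of the subcutaneous fascicles that indent the dermis. Section 9.1.2 likewise frames the secondary endpoints as changes; dermal edema and subcutaneous nodules are recorded as present or absent.
- **Visits.** Section 9.2.2 has each woman assessed twice, before and after treatment, so every comparison is within the same women.
- **Description.** Section 10.1 describes the variables in the Data Collection Notebook "with frequency tables for nominal variables and measures of central tendency and dispersion for the continuous variables", and adds: "95% confidence intervals (95% CI) will be estimated for the latter". Nominal variables get no interval.
- **Comparison.** Section 10.2 states "we will study the mean values of the trabecular structure and skin thickness, comparing the results before and after treatment". It names Student's t test for two groups with Mann-Whitney as the fallback, and Fisher's exact test for qualitative variables, all at p < 0.05. It names no mean change, SD of change or interval for a change.
- **Sample size.** Section 7.4 says "The number of subjects expected for this pilot study is 30 women". Section 7.5 says "it has been estimated that 30 patients will be sufficient to analyze results" and then that "it is understood that the estimation of the sample size is not necessary". It gives no effect size, SD, power or precision.

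**The concern.** An uncontrolled exploratory pilot is most useful for the size of the within-woman change and how much it varies between women. Read as written, the plan yields a mean and interval at each visit plus a p-value. None of these is an interval for the endpoint, and the spread of individual changes is not reported. For edema and nodules the output is two frequency tables and a p-value, with no indication of how precisely the change is known.

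A reader left with two visit intervals cannot tell a precisely estimated change from an imprecise one. Leaving the estimate unspecified also lets the choice of what to report be made after the data are seen.

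**Working it through.** **The plan's own figure.** The 30 in sections 7.4 and 7.5 cannot be reproduced, because no input to a calculation is given. The steps below show what the planned output does and does not determine.

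**Inputs.** n = 30 (section 7.4). The 95% level is from section 10.1. Tests are taken as two-sided at 5%; section 10.2 gives 0.05 without sidedness. Assumptions not in the documents: equal SDs at the two visits, before/after correlation r of 0.3, 0.7 or 0.9, and 24 or 20 complete pairs in place of 30 (section 7.7 defines dropouts but gives no rate).

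**Step 1: what can be recovered.** With complete pairs, mean change = final mean − initial mean, so the point estimate follows from the visit means. The SD does not: SD of change = visit SD × √(2(1 − r)), and visit summaries carry no information on r.

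**Step 2: interval for the change in visit SDs, n = 30.** Half-width = t(0.975, 29)/√30 × √(2(1 − r)) = 0.373 × √(2(1 − r)).

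| Assumed r | √(2(1 − r)) | Half-width (visit SD) |
|---|---|---|
| 0.3 | 1.183 | 0.44 |
| 0.7 | 0.775 | 0.29 |
| 0.9 | 0.447 | 0.17 |

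The same visit means and SDs are compatible with all three rows. An interval built from the unpaired two-group t test would be t(0.975, 58) × √(2/30) = 0.517 visit SD, whatever r is. Two separate visit intervals, each ±0.373 SD, overlap until the means differ by 2 × 0.373, about 0.75 SD. They are therefore no substitute for an interval on the change.

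**Step 3: precision in SDs of the change.** Half-width = t(0.975, n − 1)/√n, which needs no assumption on r.

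| Complete pairs | Half-width (SD of change) | Mean change with 80% power (SD of change) |
|---|---|---|
| 30 | 0.373 | 0.529 |
| 24 (20% loss, assumed) | 0.422 | 0.597 |
| 20 (assumed) | 0.468 | 0.660 |

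**Step 4: yes/no endpoints.** Let b women go from yes to no and c from no to yes. The net change is (b − c)/n, with Wald standard error √(b + c − (b − c)²/n)/n. Two illustrative cases at n = 30 have the same net fall of 6/30 = 20 points:

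- b = 9, c = 3: SE = √(12 − 1.2)/30 = 0.110; 95% CI −1.5 to 41.5 points.
- b = 6, c = 0: SE = √(6 − 1.2)/30 = 0.073; 95% CI 5.7 to 34.3 points.

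Frequency tables by visit show the same 20-point fall in both cases. Only the paired counts separate them.

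**The case against.** The strongest reply is that section 10.1 covers every variable in the notebook and never limits itself to visit values. Section 9.2.4 speaks of the evaluators assessing ultrasound changes. If a change score is entered in the notebook, 10.1 already promises its dispersion and 95% CI. The notebook is not among the documents, so this cannot be excluded. What stands is that the interval for the change is not specified; it would be wrong to say that it is ruled out.

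A second reply is that, with a paired t test, the mean change and exact p-value would let a reader work back to the SD of the change. That is true, but section 10.2 does not call its tests paired, and its stated fallback is for independent groups. Naming a paired test would still not commit the sponsor to reporting the estimate and its interval.

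Third, both visits are measured in the same women, so every interval asked for here can be computed from planned data. This stands too: the gap is in the specification, and no information is lost.

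Two stronger readings are tempting and are not supported:

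- A reader might infer that section 7.5 promises a precision that the analysis then fails to deliver. It says only that 30 suffices to analyze results, and it disclaims a calculation.
- A reader might infer that the size of the change itself is lost. With complete pairs it is the difference of the visit means; only its SD and interval are missing.

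**Conclusion.** The point holds as a gap in the specified analysis. The endpoint is a within-woman difference, yet no SD or 95% CI is specified for it, and the change in edema and nodules has no interval. Visit summaries cannot supply these: at n = 30 the half-width for the change could be 0.44, 0.29 or 0.17 visit SD, depending on a correlation that the planned output does not report. Those figures assume equal visit SDs and the stated values of r. They show sensitivity and do not predict this trial's results.

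The two sentences in section 7.5 sit badly together, since one says an estimate was made and the other that none is needed. By itself that is only missing detail. The change to section 10.2 carries more weight, because it replaces a comparison of visit means with a direct estimate of the endpoint at no cost in data.

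**What to change.** **Section 10.2.** State that the primary result is the mean within-woman change in fascicle length, with its SD and paired 95% CI. Do the same for skin thickness and the photographic scores.

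**Edema and nodules.** Report the paired change in proportion with a 95% CI for paired proportions. First state how disagreement between the two evaluators becomes a yes/no value: section 9.2.4 averages them, so one yes and one no would give 0.5.

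**Section 7.5 (optional).** Replace the two sentences with a statement that no formal calculation was done; that 30 pairs give a 95% CI half-width of 0.37 SD of the change (0.42 with 24 pairs, assuming 20% loss); and that 30 pairs give 80% power for a mean change of about 0.53 SD of the change (two-sided 5%). Label the units as SD of the change throughout. Do not give feasibility as the basis for 30 unless the sponsor confirms it, since the documents do not say so.

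**Cost.** Wording in the analysis and sample-size sections only, with no new data. The downside is that a statement of sufficiency becomes a modest precision figure.

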10.2 Analysis of objectives

For the analysis of the primary objective, we will study the mean values of the trabecular structure and skin thickness, comparing the results before and after treatment. Similarly we will compare the scores of the photographic images (overall score and scores of each scale). Qualitative variables will be compared using Fisher's exact test, and the quantitative variables will be compared by means of the student's t test (in the case of 2 groups) or by the one-way ANOVA test (for 3 or more groups). If the conditions of the Student t test or the Anova test are not met, we will use the non-parametric test of the Mann-Withney U (2 groups) or the Kruskall-Wallis test (for 3 or more groups).

For all tests, the significance level will be set at $p < 0.05$.

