1.9 Primary objective

To evaluate the structural changes (trabecular texture) in subcutaneous tissue detected by skin ultrasound in patients with cellulite after a multidisciplinary treatment that includes diet, physical exercise and cosmetic cream.

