1.10 Secondary objectives

- To evaluate changes in skin thickness assessed by skin ultrasound after multidisciplinary treatment.
- To evaluate the changes in cellulite severity in the involved areas after the multidisciplinary treatment from photographic images.

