1.13 Primary Outcome Measure

Differences in trabecular structure of subcutaneous tissue between prior to starting multidisciplinary treatment and after the end of this treatment, assessed by skin ultrasound.

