9.1.2 Secondary endpoints

- Changes in other skin structural parameters between the time prior to the multidisciplinary treatment and after the end of said treatment, assessed by skin ultrasound:
 - Thickness of skin: thickness of dermis, thickness of epidermis and total thickness of the skin
 - Changes in the echogenicity of the dermis
 - Presence of dermal edema
 - Presence of nodules in the subcutaneous areolar tissue

- Changes in cellulite severity in the areas involved, between the time prior to the multidisciplinary treatment and after the end of treatment, assessed from photographic images, using the validated photonumeric scale of Hexel et al.⁷, which evaluates the following parameters:
 - Number of visible depressions (0 = none, 1 = 1 to 4; 2 = 5 to 9; 3 = 10 or more depressions)
 - Depth of depressions (0 = No depressions; 1 = superficial depressions, 2 = medium depth depressions, 3 = deep depressions)
 - Morphology of the epidermis (0 = flat, 1 = "orange skin" look; 2 = "cottage cheese" look; 3 = quilted look)
 - Grade of laxity or sagging (0 = absence of laxity/sagging; 1 = slight; 2 = moderate; 3 = severe)
 - Severity in accordance with Nürnberg and Muller scale(0 = zero grade; 1 = first grade; 2 = second grade; 3 = third grade)

The addition of the scores obtained will provide a final score that will allow the cellulite classification:

From 1 to 5 = mild cellulite

From 6 to 10 = moderate cellulite

From 11 to 15 = severe cellulite

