9.2.4 Procedure for the assessment of skin ultrasound

Ultrasound changes will be assessed at the end of the study. The ultrasound images will be saved with the patient and the visit code. At the end of the study, ultrasound changes will be assessed by two evaluators, independently and blindly. The final result will be the average between both evaluations.

The parameters to be controlled are:

- Dermis thickness
- Hypodermis thickness
- Total skin thickness
- Dermis echogenicity
- Assess presence of dermal edema
- Presence of nodules in areolar subcutaneous tissue

- Indented subcutaneous fascicles in the dermis (length: measured from the center of the base to the point of maximum indentation in dermis)
- Presence and quantity of perpendicular fibrous septa

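### Section 10.2 analyses skin thickness under the primary objective although the plan makes it secondary, and the ultrasound reading list in 9.2.4 does not match the endpoint lists

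*Combined protocol and SAP*

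**What the plan says.** **Primary.** Sections 1.9 and 5.1 give the objective as: "To evaluate the structural changes (trabecular texture) in subcutaneous tissue detected by skin ultrasound in patients with cellulite". The outcome in 1.13 is again confined to trabecular structure: "Differences in trabecular structure of subcutaneous tissue between prior to starting multidisciplinary treatment". Section 9.1.1 lists a single measure beneath that outcome: "Indented subcutaneous fascicles in the dermis (length: measured from the center of the base to the point of maximum indentation in the dermis".

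**Secondary.** Sections 1.10 and 5.2 include: "To evaluate changes in skin thickness assessed by skin ultrasound after multidisciplinary treatment". Section 9.1.2 lists it among the secondary ultrasound endpoints: "Thickness of skin: thickness of dermis, thickness of epidermis and total thickness of the skin".

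**Analysis.** Section 10.2 opens: "For the analysis of the primary objective, we will study the mean values of the trabecular structure and skin thickness". The photographic scores follow in a separate sentence. Every test is at the 0.05 level, and no rule is given for several measures under one objective.

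**Reading list.** Section 9.2.4 names what the two evaluators assess on the saved images at the end of the study. Its thickness items are dermis, "Hypodermis thickness" and total skin. It also lists the presence and quantity of perpendicular fibrous septa.

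**The concern.** The objectives and endpoints give one hierarchy, and the only section that governs the analysis gives another. Section 10.2 names no other analysis of thickness, so the secondary thickness objective is dealt with only under the primary one. An analyst who follows 10.2 could present a thinner or thicker skin as a primary result, and one who follows 9.1.1 could not.

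The second problem is measurement. Evaluators who follow 9.2.4 would not record epidermis thickness, which is a stated endpoint. They would record hypodermis thickness and septa, whose place among the endpoints is not stated. Because one list has epidermis and the other hypodermis, it is also unclear which layers total skin thickness covers. Septa could be taken as part of trabecular structure, the term that 10.2 uses without repeating the fascicle-length definition.

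**Working it through.** **1. Hierarchy, side by side**

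| Section | Trabecular structure / fascicle length | Skin thickness |
|---|---|---|
| 1.9, 5.1 (primary objective) | primary | not mentioned |
| 1.13 (primary outcome) | primary | not mentioned |
| 9.1.1 (primary endpoint) | primary, fascicle length only | not mentioned |
| 1.10, 5.2 (secondary objectives) | not mentioned | secondary |
| 9.1.2 (secondary endpoints) | not mentioned | secondary |
| 10.2 (analysis) | under the primary objective | under the primary objective |

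Only 10.2 disagrees.

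**2. Ultrasound measures, endpoint lists against reading list**

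| Measure | 9.1.1 / 9.1.2 | 9.2.4 |
|---|---|---|
| Fascicle length | yes | yes |
| Dermis thickness | yes | yes |
| Total skin thickness | yes | yes |
| Dermis echogenicity | yes | yes |
| Dermal edema | yes | yes |
| Subcutaneous nodules | yes | yes |
| Epidermis thickness | yes | **no** |
| Hypodermis thickness | **no** | yes |
| Perpendicular fibrous septa | **no** | yes |

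The endpoint lists hold 6 + 1 = 7 measures and the reading list 6 + 2 = 8. Six are common to both, out of 6 + 1 + 2 = 9 distinct measures.

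**3. What the 10.2 wording could do to the error rate**

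The plan has no figure to reproduce: 7.5 gives 30 women without an effect size, standard deviation or power. The rates below assume that any one significant measure counts as success, which the plan does not say. They also assume two-sided tests, no true change in any measure, and a common correlation between measures. The documents give no correlation.

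*Tests of correct 5% size.* For k independent tests the chance of at least one false positive is 1 − 0.95^k:

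- k = 2 (fascicle length and one thickness): 1 − 0.95² = 0.0975
- k = 4 (fascicle length and the three thicknesses of 9.1.2): 1 − 0.95⁴ = 0.1855

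For correlation ρ between measures, the chance is 1 − ∫ [Φ((c − √ρ z)/√(1−ρ)) − Φ((−c − √ρ z)/√(1−ρ))]^k φ(z) dz with c = 1.96. Numerical integration gives:

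| ρ | 0 | 0.3 | 0.5 | 0.7 | 0.8 |
|---|---|---|---|---|---|
| k = 2 | 0.0975 | 0.0951 | 0.0907 | 0.0835 | 0.0781 |
| k = 4 | 0.1855 | 0.1740 | 0.1558 | 0.1304 | 0.1141 |

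*The test that 10.2 names.* Section 10.2 names the t test for two groups. If that is applied literally to before/after data, it ignores the within-woman correlation r and becomes conservative, because the true standard error of the change is smaller by a factor √(1−r). The table shows the simulated chance of any significant result with 30 women at each visit and 200,000 trials per setting. In each pair, the first figure is for independent measures and the second for a correlation of 0.8 between measures.

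| r | one test | k = 2 | k = 3 | k = 4 |
|---|---|---|---|---|
| 0.3 | 0.0202 | 0.0400 / 0.0327 | 0.0592 / 0.0424 | 0.0784 / 0.0504 |
| 0.5 | 0.0069 | 0.0138 / 0.0114 | 0.0203 / 0.0151 | 0.0272 / 0.0184 |
| 0.7 | 0.0007 | 0.0014 / 0.0014 | 0.0020 / 0.0019 | 0.0028 / 0.0023 |

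In this reading the rate is clearly above 5% only at r = 0.3 with three or four independent measures. Four measures correlated at 0.8 give about 5.0%, and three give 4.2%.

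**The case against.** The strongest reply is that the hierarchy is not really in doubt. Objectives, primary outcome and endpoints agree, and one clause in 10.2 does not. That section covers all objectives under one heading and may simply group by method, ultrasound first and then photographs. This may well be how the sentence arose. As written, though, it names the primary objective and puts thickness inside it, and 10.2 is the section an analyst will follow.

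Three narrower replies concern the lists:

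- **Septa.** Section 9.1.1 ties trabecular structure to fascicle length, so reading septa into the primary measure is a stretch. This largely stands, and one explicit sentence would settle it.
- **Unassigned measures.** Section 10.1 plans descriptive statistics for every variable in the data collection notebook. Hypodermis and septa would therefore have a descriptive role if their readings are entered there, which the documents do not spell out. That is still not endpoint status.
- **Epidermis.** The mismatch with hypodermis may be a one-word slip, but the documents do not show which word was meant. Epidermis thickness could be obtained as total minus dermis if total means those two layers only, but total is undefined. The omission can be repaired, since the images are saved and read at the end, provided they show that layer.

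Finally, the study is an uncontrolled pilot, described in 7.5 with the words "In an exploratory pilot study to test a concept", and the error rates depend on a success rule it does not state. Both points stand. They limit the size of the harm and leave the contradiction in place.

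**Conclusion.** The concern holds, and the plan is wrong as written on both counts. Section 10.2 contradicts 1.9, 1.10, 1.13, 5.1, 5.2, 9.1.1 and 9.1.2 on the status of skin thickness. Section 9.2.4 differs from the endpoint lists on three of nine ultrasound measures. Confidence is high because both points can be read directly from the current text.

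The practical consequence is unclear reporting: a secondary measure presented under the primary objective, and a stated endpoint left unread. No inflation of the error rate is established. The range of 7.8% to 18.5% needs a success rule based on any one measure, correctly sized tests and assumed correlations. The two-group test, taken literally, mostly gives less than 5%. Whether epidermis can be measured on the saved images is not stated. The correction should be made, but the contradiction does not undermine the study.

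**What to change.** 1. **Section 10.2.** Reword the first sentence so that the primary objective is tested only on the before/after change in fascicle length, as defined in 9.1.1. Move skin thickness to the secondary analyses and report it as exploratory, with a 95% confidence interval for the change. Section 10.1 promises intervals for continuous variables but does not say they are for the change.
2. **Sections 9.1.2 and 9.2.4.** Before the end-of-study reading, merge these into one list that gives epidermis, hypodermis and septa each a stated status. Septa should be explicitly outside the primary test unless 9.1.1 is changed. State which layers make up total skin thickness.
3. **Sponsor confirmation.** The sponsor should confirm that every listed layer can be measured on the saved images.

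The cost is wording in three sections and one confirmation, with no added patients or visits. The price to the sponsor is that a change in thickness can no longer count as primary evidence.

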1.8 Study design

Prospective, no controlled pilot study on the structural changes in subcutaneous tissue observed by skin ultrasound, in patients with edematous fibrosclerotic panniculopathy (cellulite) after a multidisciplinary treatment program including diet, physical exercise and cosmetic cream.

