9.2.2 Follow-up of patients

Patient follow-up will be 10 ± 1 weeks to 18 ± 1 weeks, depending on duration of treatment depending on the degree of cellulite.

Only two controls will be performed: initial (prior to the multidisciplinary treatment) and final (after the end of the multidisciplinary treatment).

Initial visit

The inclusion and exclusion criteria will be assessed and the signed informed consent will be obtained. Demographic data (age) are recorded and the degree of cellulite is evaluated following the Nürnberg and Muller scale (0 = zero grade, 1 = first grade, 2 = second grade, 3 = third grade). The dermatologist will perform skin ultrasound and will take pictures.

Final visit

The dermatologist evaluations will be repeated: evaluation of the cellulite grade, accomplishment of skin ultrasound and photographic images.

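### Section 10.2 compares the same women before and after treatment but names no paired test; its rank and exact tests assume independent groups

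*Combined protocol and SAP*

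**What the plan says.** Section 1.8 describes a "Prospective, no controlled pilot study on the structural changes in subcutaneous tissue observed by skin ultrasound"; Sections 6.2 and 6.3 give randomization and control as not applicable. Section 9.2.2 fixes the measurement times: "Only two controls will be performed: initial (prior to the multidisciplinary treatment) and final (after the end of the multidisciplinary treatment"). Each woman therefore contributes one pair of values per variable. Section 9.1.1 defines the primary endpoint as a before-to-after difference, measured as the length of the subcutaneous fascicles indenting the dermis.

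Section 10.2 sets out the analysis as "comparing the results before and after treatment", and treats the photographic scores in the same way. The tests it names are:

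- "Qualitative variables will be compared using Fisher's exact test";
- "the quantitative variables will be compared by means of the student's t test (in the case of 2 groups"), or one-way ANOVA for three or more groups;
- if the conditions for these fail, "we will use the non-parametric test of the Mann-Withney U (2 groups) or the Kruskall-Wallis test (for 3 or more groups").

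The significance level is 0.05. No paired t test, signed-rank test, McNemar test or repeated-measures method appears anywhere in the supplied text.

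**The concern.** Two readings of the same woman are not independent. Mann-Whitney U and Fisher's exact test treat the before and after values as if they came from two separate sets of women, so they use the wrong reference distribution. The t test could be run either way: the text does not call it unpaired, but the reference to two groups and the choice of Mann-Whitney U as its fallback both point to the independent-samples version.

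Section 10.2 contains the plan's only inferential analysis, and it covers the primary endpoint. Two things are at stake. A real change may be missed because the test ignores the pairing. And two analysts who follow the section in good faith could report different p-values for the primary endpoint from the same data.

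**Working it through.** The plan states no power, SD or effect size (Section 7.5 says a sample size estimate is unnecessary), so there is no figure to reproduce. The size of the problem can only be shown as a range.

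**Inputs.** From the documents: n = 30 women (Section 7.4), two visits (Section 9.2.2), significance level 0.05 (Section 10.2). Assumed: two-sided testing, normal data, equal SDs at both visits, a change d = 0.5 SD, and r from -0.3 to 0.7.

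**Why the unpaired test goes wrong.** In SD units, the true standard error of the mean change is √(2(1 − r)/n). The unpaired test works with about √(2/n).

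- At n = 30 the unpaired standard error is √(2/30) = 0.258. At r = 0.5 the true one is √(1/30) = 0.183.
- The ratio is √(1 − r) = 0.707. The nominal cut-off of 2.002 (58 degrees of freedom) therefore acts as a cut-off of 2.002/0.707 = 2.83 true standard errors.

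**Power of the paired t test.** Noncentral t with 29 degrees of freedom, cut-off 2.045 and noncentrality d√n/√(2(1 − r)):

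- r = 0: 0.5 × 5.477/1.414 = 1.94, power 46.5%
- r = 0.3: 2.31, power 60.9%
- r = 0.5: 2.74, power 75.4%
- r = 0.7: 3.54, power 92.7%

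**t tests side by side** (unpaired figures by simulation):

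| r (assumed) | Type I error, unpaired t | Power, unpaired t | Power, paired t |
|---|---|---|---|
| -0.2 | 7.3% | 48% (test exceeds its 5% level) | 40% |
| 0 | 5.0% | 48% | 47% |
| 0.3 | 2.0% | 47% | 61% |
| 0.5 | 0.7% | 47% | 75% |
| 0.7 | 0.1% | 47% | 93% |

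At r = -0.3 the type I error of the unpaired test is about 8.4%.

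**Rank tests**, same setting, power of Mann-Whitney U against Wilcoxon signed-rank: 46% and 46% (r = 0), 44% and 59% (r = 0.3), 44% and 74% (r = 0.5), 44% and 92% (r = 0.7).

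**Presence/absence items.** Take an invented example: a feature present in 18/30 women before and 10/30 after. Fisher's exact test on these two proportions gives p = 0.069 however the women pair up. The exact McNemar test uses only the women who changed:

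| Improved / worsened | Exact McNemar p |
|---|---|
| 8 / 0 (most favourable pairing) | 0.008 |
| 10 / 2 | 0.039 |
| 11 / 3 | 0.057 |
| 12 / 4 (no association between visits) | 0.077 |

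Fisher's test could also be run on the before-by-after cross-table, but it then tests association between visits, not change. With 14 women positive at both visits, 4 who lost the feature, 4 who gained it and 8 negative at both, prevalence is 18/30 at each visit. Fisher gives p = 0.024; McNemar gives p = 1.0.

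**The case against.** The best defence is that the first-line primary analysis is not shown to be wrong. The endpoint is a continuous length, Section 9.1.1 defines it as a difference, Section 9.2.4 speaks of assessing changes, and Section 10.2 never calls the t test unpaired. This stands: if the t test is run as paired, the first-line primary test is sound, and what remains wrong is its fallback and the qualitative test.

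A second defence is that the wording about two, or three or more, groups is a generic list meant partly for comparing cellulite grades. With only two visits, ANOVA and Kruskal-Wallis could not apply to the before/after contrast in any case. But no comparison between grades is a stated objective in Section 5, and on that reading the before/after comparison would have no named test at all.

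Third, the magnitudes rest on assumed values of r and d, and the binary tables are constructed. That is also true. Nothing in the documents suggests a negative r, so the inflated type I errors mark the edge of the range rather than an expected case, and McNemar can be no better than Fisher when the two visits are unrelated.

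Finally, this is an exploratory pilot with no power claim. But Section 10.2 still sets formal tests at 0.05, and those tests should fit the design.

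**Conclusion.** The concern holds, with high confidence, and should be corrected before analysis. Mann-Whitney U and Fisher's exact test are wrong as written for the before/after comparisons. The t test is ambiguous rather than demonstrably wrong.

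These two tests are likely to be reached. The photographic items are scored 0 to 3, only 30 women are planned, and dermal edema and nodules are recorded as present or absent.

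For positive r the consequence is lost power: 14 percentage points at r = 0.3 (61 − 47), 28 at r = 0.5 (75 − 47) and 46 at r = 0.7 (93 − 47), for an assumed 0.5 SD change in 30 pairs. At r = 0 there is no loss; only a negative r would inflate the type I error. The descriptive 95% confidence intervals in Section 10.1 are not affected, and no stated power is contradicted.

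**What to change.** Reword Section 10.2 to specify, for every before/after comparison:

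- **Quantitative variables:** paired t test, reporting the mean within-woman change, its SD and its 95% confidence interval.
- **Fallback, and the ordinal 0 to 3 photographic items:** Wilcoxon signed-rank test.
- **Presence/absence items** (dermal edema, nodules): exact McNemar test, reporting the numbers improved and worsened.
- **Any item with more than two unordered categories**, if dermal echogenicity is recorded that way: a test of marginal homogeneity.
- **ANOVA or Kruskal-Wallis:** keep only for comparing within-woman change between cellulite grades, if that is wanted.

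Add one sentence to Section 9.2.4. It now says "ultrasound changes will be assessed by two evaluators, independently and blindly. The final result will be the average between both evaluations". For an item such as "Presence of dermal edema" a split reading averages to 0.5, which neither McNemar nor Fisher can use. State a rule, for example consensus between the two evaluators, reached while still blinded.

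**Cost.** One paragraph and one sentence; no added visits, measurements or patients. Images are saved under patient and visit codes (Sections 9.2.4 and 13.1), so pairs can be linked; for the recoded photographs the recoding key must be kept. Consensus is needed only for split readings. If the evaluators agree on a proportion a of images (assumed), each item has 60(1 − a) split images, in 30(1 − a²) women: 3 images in about 3 women at a = 0.95, and 12 images in about 11 women at a = 0.80.
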